### **Benchmarks**

This study is being conducted to validate specific cognitive-affective targets for use in larger prevention studies. As such, documenting a significant effect of interventions on delay discounting and distress tolerance represents a go/no go criterion for future study (Aim 2). Also, to encourage study of the modification of these targets in a larger scale (R01) environment, documentation of significant benefit on proximal measures of smoking risk/behavior is needed (Aim 3). Success with these benchmarks, in a design with adequate feasibility/acceptability would document the need for R01 study in a prevention trial with longitudinal follow-up.

Statistical Analysis Plan for
R21DA041531 - Rescuing Cognitive and Emotional Regulatory
Processes to Aid Smoking Prevention
Version Date: July 16, 2019

Data Analysis

Analyses for outliers, non-normal distributions, nonlinear relations, and influence statistics will be conducted; data transformation will be considered where appropriate. We will examine missing data patterns and dropout rates and will use pattern mixture modeling to evaluate the influence of missing data on the results.¹⁴⁷ We will use multilevel modeling (MLM) to analyze the data because it is an intent-to-treat analysis that includes all participants (which maximizes power and generalizability). We will use an ANOVA model (performed using MLM) for the repeated measures over time because the change in the DVs over time may not be linear. The 3 treatment conditions will be coded using 2 dummy variables contrasting each active treatment with control. Time will be alternately centered at post-treatment or follow-up so that the dummy variable contrasts will reflect group differences at those time points. All models will include relevant covariates (e.g., parental smoking (dummy coded since it is categorical), peer smoking, and sensation seeking). Since the relation between the covariates and outcome may differ among treatment conditions (e.g., the relation between parental smoking and smoking risk may be lower in WM+ SPII than in C+SPII), interaction terms will allow these relations to vary across treatment conditions. Non-significant interaction terms will be dropped.

1. The feasibility/ acceptability of school- and community-based brief interventions will be assessed by recruitment and attendance rates across the study period; acceptability (attendance of 80% of interventions by 70% of the randomized sample) will be assessed across the 3 conditions.
2. We hypothesize that the WM+SPII and DT+SPII interventions, relative to C+SPII, will lead to higher WM and higher DT, respectively. Further, we expect that WM will be higher in WM+SPII than in DT+SPII, and that DT will be higher in DT+SPII than in WM+SPII. The latter contrast will indicate if the two active treatments differ from each other on WM and/or DT; to perform these latter analyses, we will replace the dummy variable contrasting WM+SPII and C+SPII, with a dummy variable comparing WM+SPII to DT+SPII.
3. To evaluate the impact of cognitive/affective target activation on proximal smoking risk/behavior following intervention, WM and DT will be added as time-varying predictors (TVPs) of outcome in MLM models for each of the 3 measures of smoking risk (susceptibility to smoking, implicit attitudes toward smoking, and delay discounting) and for actual smoking behavior (smoking behavior is dichotomous, so it will be analyzed using a GLMM with a logistic linking function). Because TVPs conflate the between-subjects and within-subjects components of the predictor, we will disaggregate each TVP into the participant's average level of the TVP across assessments, and their deviations from their average level, at each assessment. The regression coefficients for WM and DT predicting outcome in these models will indicate the degree to which each is related to smoking risk. The "deviations" component of the TVP will calculate the relation between both WM and DT with proximal measures of smoking risk within-subjects over time.

Power Analysis.

We used PinT 2.12 (Power in Two-Level Models)¹⁴⁸ to calculate the smallest effect size detectable with .80 power for each Aim. We assumed 150 total participants with 33% missing data (MLM and GLMM include all participants regardless of missing data, but the power is affected by number of obtained assessments per participant). We also assumed 6 covariates in each of the models. Alpha was set at .05. Aims 2 and 3: We have greater than .80 power to detect an effect size of $d = .29$ or larger for the MLM analyses. We have greater than .80 power to detect an effect size $\omega = .23$ or larger (between a small, $\omega = .10$, and a medium, $\omega = .30$ effect size) for the GLMM analysis (actual smoking behavior).

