## **APPROACH**

### **Design Overview and Considerations**

We are targeting a high-risk (low SES adolescents) population at a highly relevant period (high school) for smoking onset. The study design calls for block randomization of 150 non-smoking adolescents to one of three intervention conditions: (1) a control condition offering health education combined with a smoking prevention informational intervention (C+SPII), (2) a WM intervention delivered prior to a smoking prevention informational intervention (WM+SPII), (3) a DT training intervention delivered prior to a smoking prevention informational intervention (DI+SPII). Smoking risk proximal outcomes are assessed by smoking propensity self-report, delay discounting, and implicit associations to smoking; Smoking behavior is assessed at one-month follow-up.

- **Why Utilize a SPII as a component common to all randomized conditions?** Meta-analytic review indicates that smoking prevention informational interventions can offer benefits, but there is also evidence these benefits are limited for low-SES participants. Our interventions are designed to enhance the ability of individuals to utilize standard SPIIs (by enhancing cognitive and affective self-control skills), and hence, are designed to rescue prevention outcomes for these at-risk individuals.
- **Why block randomize by parental smoking?** Parental smoking is associated with smoking attitudes among children and confers a significantly higher risk of smoking initiation. Crucially, research indicates that parental smoking is one significant mechanism by which low SES translates into youth smoking. Ensuring balance of parental smoking status across the intervention conditions allows evaluation of potential

moderating effects of this factor on interventions and outcomes.

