adolescents' behavioral problems and self-regulatory ability, as well as the impact of poverty on WM ([name] & Evans, 2012), and health outcomes including smoking, and body mass index. [name] has extensive experience with proof-of-concept intervention studies and subsequent large-scale trials in specialty psychiatric as well as substance abusing populations, including smokers (ongoing: ; ongoing R34 DA034658; recently completed R21 DA030808). [name] is also experience with conducting successful cognitive training interventions, as well as neuropsychological assessment studies for specialty populations ranging from those with depression to schizophrenia and illicit substance abuse. The co-PIs will also receive help from the consultant team (1) [name]: leading expert in the study of negative affectivity and DT on smoking outcomes, (2) [name], a foremost expert on the association between delay discounting, WM, WM training, and addictive behavior including smoking, and [name], an expert statistician who has been a regular collaborator with both Drs. [name] and [name].

**Interventions.** Participants will be randomized to 1 of 3 study conditions according to two block randomization factors: sex and parental smoking status. Each intervention is to be delivered over eight consecutive weeks. Interventions are to be led by the Project Director, with ongoing supervision from Drs. [name] and [name]. Although online training is available for mindfulness, and provides an excellent potential for aiding dissemination in a subsequent prevention study, we are conducting in-person mindfulness training to help reduce the impact of differential computer skills on the uptake of skills. For WM training, a computer program is used, but the Project Director will be present to facilitate use of the computer and work through the module.

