**Parental and Peer smoking.** We will assess four categories of exposure to parent smoking: (1) both parents nonsmokers: (2) both parents former smokers or, one former smoker and one nonsmoker: (3) one parent a current smoker: the other a nonsmoker or a former smoker: (4) both parents current smokers. Affiliation with peers who smoke is a strong psychosocial predictor of smoking initiation and current smoking,

and will be measured by summing responses to three items asking whether the adolescent's best friend smokes and how many of his or her other four best male and four best female friends smoke (range 0 to 9 friends smoking).

**Sensation Seeking (SS).** SS is positively associated with smoking onset, as well as heavier smoking and poorer cessation adherence and success. We will use the Sensation Seeking Scale, as it has been used with acceptable reliability with low-income minority youth.

**Smoking Susceptibility.** Consistent with previous work we will measure smoking susceptibility with two items (e.g., "Have you ever been curious about smoking a cigarette: 0 = No, 1 = Yes") from the pan-Canadian Youth Smoking Survey, and three items repeatedly used in the literature (e.g., "If one of your best friends were to offer you a cigarette, would you smoke it: 0 = Definitely no, 3 = Definitely yes"; e.g.,) to create a single composite score that is the sum of these five items providing a continuous score ranging from 0 (no susceptibility) to 11 (highest susceptibility).

**Smoking IAT:** We will use a smoking-specific implicit association test (IAT) that assesses implicit cognitive associations between smoking and negative vs. positive social consequences. This version of the IAT successfully predicted odds of smoking abstinence over and above the effects of other relevant predictors.

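### The arm contrasts on continuous outcomes are not stated to adjust for the baseline outcome or for sex, a randomisation factor, which gives up precision at almost no saving

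*SAP*

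**What the plan says.** The SAP's Data Analysis section specifies a repeated-measures ANOVA fitted by multilevel modelling. On treatment coding it says: "The 3 treatment conditions will be coded using 2 dummy variables contrasting each active treatment with control". On the effect to be read from the model it says: "Time will be alternately centered at post-treatment or follow-up so that the dummy variable contrasts will reflect group differences at those time points".

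On adjustment it says: "All models will include relevant covariates (e.g., parental smoking (dummy coded since it is categorical), peer smoking, and sensation seeking". Covariate-by-treatment interactions are added and dropped if not significant. The baseline value of the outcome is not named, no equality of arm means at baseline is imposed, and sex is not mentioned.

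The protocol's Interventions paragraph allocates participants using "two block randomization factors: sex and parental smoking status". Its Design Overview explains the choice of the same three covariates as the SAP and does not include sex.

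The assessment schedule (protocol, Table 1) collects every continuous outcome at baseline. Working memory (WM) and distress tolerance (DT) are measured at baseline and 1 week only. Susceptibility, the smoking IAT and delay discounting are measured at baseline, 1 week and 1 month.

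**The concern.** It is easy to assume that a multilevel model containing the baseline visit has adjusted for baseline. It has not, if each arm has its own free mean at each visit. The arm dummy at the centred visit is then the difference in means at that visit, apart from the named covariates, and the baseline outcome contributes nothing when data are complete.

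For WM and DT this follows almost directly from the schedule. With only two visits, a repeated-measures model must use baseline as a response level, because otherwise a single measurement remains.

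The stake is power. The protocol's Benchmarks section makes significant intervention effects on its targets a go/no-go criterion, and also asks for significant benefit on the proximal risk measures. With three arms sharing 150 participants, discarding a prognostic measurement already in hand makes a false no-go more likely. The protocol itself justifies its covariates by precision, and the baseline outcome is a natural candidate on that ground.

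**Working it through.** **Inputs.** From the documents: 150 participants and three arms (protocol, Design Overview); alpha .05, power .80, 33% missing data, 6 covariates and a stated detectable effect of d = .29 (SAP, Power Analysis). Assumed: equal allocation (50 per arm), two-sided alpha, outcome SD of 1, and a baseline-outcome correlation ρ, for which the documents give no value.

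**The plan's own figure.** For one active arm against control:

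- MDE = (1.960 + 0.842) × √(2/n).
- n = 50 gives 2.802 × .200 = .560.
- n = 33.5 (33% lost) gives 2.802 × .244 = .685.

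The stated d = .29 does not come out as an arm contrast in this way; power at .29 is 30.5% with 50 per arm and 22.0% with 33.5. Baseline adjustment alone would reach .29 only at ρ = √(1 − (.29/.560)²) ≈ .86, or about .91 with 33.5 per arm. The power software cannot be rerun, because the documents give no variance components or number of visits. The present point does not depend on that figure.

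**Does baseline as a response level help?** Simulation: 100 data sets per ρ, three arms of 50, three visits, random-intercept model with arm × time centred at post-treatment, no covariates, complete data. The arm coefficient equalled the difference in post-treatment means to about 1e-14. Its mean SE was .199 at ρ = .5 and .200 at ρ = .7, against a theoretical √(2/50) = .200. With baseline means constrained equal, the SE was .172 and .143, ratios of .87 and .71. Theory gives √(1 − ρ²) = .866 and .714.

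**Size with complete data, 50 per arm.** Variance is multiplied by 1 − ρ², and the MDE by √(1 − ρ²).

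| ρ (assumed) | Variance cut | MDE | Power at an illustrative d = .5 |
|---|---|---|---|
| no adjustment | – | .560 | 70.5% |
| .3 | 9% | .535 | 74.6% |
| .5 | 25% | .485 | 82.3% |
| .7 | 49% | .400 | 93.8% |

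**Size with 33% post-baseline dropout** (same simulation, both later visits lost). Here the free-means model does borrow something from baseline, so the gap narrows.

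- ρ = .5: SE .233 against .211. Variance cut 1 − (.211/.233)² ≈ 18%. MDE 2.802 × SE falls from about .65 to .59.
- ρ = .7: SE .226 against .176. Variance cut ≈ 39%. MDE falls from about .63 to .49.

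**After the named covariates.** The relevant ρ is the one that remains once they are in the model. For illustration, suppose they explain 10% or 20% of variance, equally at both visits. A raw ρ of .6 then becomes (.6 − .1)/.9 = .56 or (.6 − .2)/.8 = .50, and the complete-data cut goes from 36% to 31% or 25%.

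**Sex.** If sex explains 1%, 5% or 10% of outcome variance (assumed), the MDE with 50 per arm is .560 × √(1 − R²) = .558, .546 or .532.

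**The case against.** The strongest reply is that the plan is silent rather than committed. The covariate list is given by example. The power section assumes six covariates. Four parental-smoking categories make three dummies, and peer smoking and sensation seeking bring the named terms to five, so the sixth could be sex or the baseline outcome. This stands in part: omission is inferred, and an open list is itself part of the defect. It does not settle the matter for WM and DT, where baseline already has to be a response level, and nothing says that arm means are held equal there.

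A second reply is that complete-data figures flatter the gain, since the plan expects 33% missing data and already adjusts for three covariates. That stands, and it is why the dropout figures are given alongside.

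A third is that a blanket remedy would do harm. Aim 3 splits WM and DT into a person mean and deviations from it. Taking baseline out of those models would leave one WM and DT value per person and no deviation to estimate. Baseline adjustment also has no role for actual smoking, because participants are meant to be non-smokers at entry. Both limits stand and shape the fix.

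A reader might infer that the contrast is a raw difference, or that chance baseline imbalance biases it. The documents support neither. Three covariates enter every model, one of them the other randomisation factor. Under randomisation the post-treatment difference is unbiased, and its standard error already allows for chance imbalance.

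**Conclusion.** The point holds as a loss of efficiency, not as an invalid analysis. As written, the arm contrasts on continuous outcomes are visit-specific group differences adjusted for parental smoking, peer smoking and sensation seeking, but not stated to be adjusted for the baseline outcome or for sex.

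Nearly all of the recoverable precision lies in the baseline outcome. The gain is modest if ρ is near .3 and substantial at .5 to .7; under the planned level of missing data, roughly 18% to 39% of the variance at ρ of .5 to .7 is the fairer range. These sizes rest on an assumed ρ, equal allocation, and simulations without covariates, so the realised gain may be smaller. Naming sex mainly aligns the analysis with the randomisation; no document shows that sex strongly predicts these outcomes, and the expected gain is small.

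**What to change.** For the arm contrasts on continuous outcomes, state one of two models:

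- A longitudinal model with baseline means constrained equal across arms. For WM and DT, fit time plus arm × post. For susceptibility, IAT and delay discounting, fit time plus arm × post and arm × follow-up. The WM-against-DT comparison is then the difference between two arm coefficients.
- ANCOVA with the baseline outcome as a covariate, which gives essentially the same precision when data are complete.

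If covariate-by-treatment interactions are kept in the constrained model, let them act only after baseline, so that the equality of baseline means is preserved.

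Replace the list given by example with a closed one that includes sex alongside parental smoking in these models.

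State two exceptions. Keep baseline as a response level in the Aim 3 time-varying-predictor models, and do not apply baseline adjustment to the dichotomous smoking outcome.

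The cost is SAP wording and one or two degrees of freedom. No new data are needed.

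### Keeping only the significant covariate-by-arm interactions makes the meaning of the Aim 2 arm contrasts depend on chance and, unless every covariate is centered, raises their type I error above .05

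*SAP*

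**What the plan says.** SAP, Data Analysis, sets up the arm comparison in this way: "The 3 treatment conditions will be coded using 2 dummy variables contrasting each active treatment with control". Time is centered at post-treatment or at follow-up so that these dummies give the group difference at that visit. Parental smoking (dummy coded), peer smoking and sensation seeking are named as examples of the covariates in every model. The section adds that "interaction terms will allow these relations to vary across treatment conditions", and closes the matter with "Non-significant interaction terms will be dropped".

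The Protocol (Assessments, Parental and Peer smoking) says "We will assess four categories of exposure to parent smoking" and scores peer smoking from 0 to 9. SAP, Power Analysis, says "We also assumed 6 covariates in each of the models" and "Alpha was set at .05".

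The SAP does not state:
- whether covariates other than time are centered;
- the retention threshold or the order of elimination;
- whether terms are tested singly or jointly per covariate;
- an arm contrast averaged over the covariates.

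**The concern.** The two arm dummies carry the Aim 2 hypotheses, and the Protocol's Benchmarks section makes a significant intervention effect a go/no-go criterion for further study. Under the rule as written, the data decide, outcome by outcome, whether an arm dummy means the average effect or the effect in some corner of the covariate space. The term that brings about this change is kept because its own estimate is extreme. With off-center coding that estimate is strongly correlated with the arm dummy, so the dummy's p-value need not hold the stated .05. At stake are the interpretation of the contrasts and the error rate of the test that decides whether the programme continues.

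**Working it through.** **1. The plan's own figures.** The only stated error rate is .05. The SAP gives none for the selection procedure, so there is no figure of that kind to reproduce. The stated detectable effect of d = .29 cannot be confirmed or refuted. A simple two-arm comparison gives (1.96 + 0.84) × √(2/50) = 0.56. With 150 × 0.67 / 3 = 33.5 per arm it gives 2.80 × √(2/33.5) = 0.68. The repeated-measures calculation needs variance components that the documents do not give. This point does not rest on d = .29.

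**2. Inputs.** From the documents: "block randomization of 150 non-smoking adolescents to one of three intervention conditions"; "We assumed 150 total participants with 33% missing data"; two arm dummies; four parental categories, hence 3 dummies; one peer score; one sensation-seeking score. Assumed: equal allocation, two-sided tests, retention at p < .05, parental categories 45/20/25/10%, mean peer smoking about 1-2, sensation-seeking mean 2 to 3.5 SD above zero, covariate slopes 0.2, within-person correlation 0.5. Simulations used N = 150 and N = 100.

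**3. How often a spurious term is kept.** The named covariates give 3 + 1 + 1 = 5 columns, so 5 × 2 = 10 interaction terms. With independent tests, 1 − .95^10 = .40. Six covariates would give 12 terms and 1 − .95^12 = .46. Simulated term-by-term selection kept at least one term in about 35-40% of null datasets with 10 terms, and in up to 48% with six covariates. Joint tests per covariate kept one in about 14%.

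**4. What the arm dummy then estimates.** Write the mean as b0 + b1·A1 + b2·A2 + g·X + d1·A1·X + d2·A2·X. The effect of arm 1 against control at covariate value X is b1 + d1·X, and the average effect is b1 + d1·X̄. Testing b1 tests the average effect only if d1 is out of the model or X̄ = 0. For a parental dummy, X = 0 is the reference category. For peer smoking it is no smoking friends.

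**5. Why selection carries over to the test.** Take one covariate with a separate slope in each arm, and let r = mean/SD.
- Relative to the centered contrast, the standard error of b1 is multiplied by √(1 + r²): √5 = 2.24 at r = 2, and √13.25 = 3.64 at r = 3.5.
- The correlation between the estimates of b1 and d1 is −r/√(1 + r²): −0.89 and −0.96.

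Keeping the term because d1 is extreme therefore tends to select datasets in which b1 is extreme. At r = 0 the correlation is zero.

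**6. Simulated type I error per arm contrast** (no arm effect and no interaction; nominal .05):

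| Model and coding | Rule | Type I error |
|---|---|---|
| No interactions | – | .044-.058 |
| All interactions kept | no selection | .039-.057 |
| Raw, one time point | one-step | .095-.102 |
| Raw, one time point | backward | .108-.128 |
| Raw, one time point | joint test per covariate | .082-.086 |
| Raw, repeated measures | one-step | .077-.097 |
| Raw, repeated measures | backward | .092-.108 |
| Only sensation seeking standardized | selection | .064-.080 |
| Only continuous covariates centered | selection | .055-.072 |
| All covariate columns centered | selection | .047-.064 |

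There were 3,000 runs per setting at one time point, 1,500 for repeated measures, and 2,000 for the continuous-only row (50 per arm). With 1,500 runs the simulation standard error near .05 is √(.05 × .95 / 1500) = .006. At one time point, given that a term was kept, rejection was .17-.29 with raw coding and .05-.08 with full centering.

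**7. Change of reference arm.** For WM+SPII against DT+SPII the SAP swaps one arm dummy. Term-by-term retention depends on the reference arm. In 22-27% of null datasets the two codings kept interactions for different covariates, even with full centering. Comparisons on one outcome could then come from different models.

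**The case against.** The SAP does not say that covariates will enter raw, and silence on centering is not a decision against it. With every column mean-centered, the error is about 5-6%, so one added sentence would restore it. Joint tests retain spurious terms much less often than term-by-term tests. The largest driver, how far the sensation-seeking mean lies from zero, is an assumption, because the documents give no scoring range. Zero smoking friends lies inside the stated range and the parental reference category is an observed group, so those contrasts are not extrapolations. In Aim 3 the coefficients of interest belong to WM and DT as time-varying predictors, and the simulations do not address them. The Protocol also gives moderation by parental smoking as a reason for blocking on it, so the interactions have a purpose.

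All of this stands as a limit on size and reach. It does not remove the defect, because the drop rule is stated outright and dummy coding of parental smoking is the stated coding. Centering only the continuous covariates leaves .055-.072, and full centering does not cure the dependence on the reference arm.

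A reader might infer more than the documents support:
- **That the plan more than doubles its type I error.** This appeared mainly with raw covariates and backward elimination, and the SAP fixes neither.
- **That fitting interactions is itself the fault.** Keeping all of them gave about .05.
- **That the power model left these terms out.** The SAP says six covariates without listing them.
- **That the chance of at least one false positive across the two contrasts (.14-.23 raw, .09-.11 centered) is all due to selection.** Part of it is the ordinary multiplicity of two tests.

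**Conclusion.** The concern holds as a defect of the stated rule, with a size that depends on choices the SAP leaves open. A kept interaction changes the arm dummy from the average effect to a reference-category or zero-covariate effect, and under the null chance alone decides which outcomes are affected. Per-contrast type I error rises from .05 to about 8-13% with raw covariates, to about 6-8% with partial centering or with only sensation seeking standardized, and stays at about 5-6% with full mean-centering. These figures rest on the assumed covariate distributions and on retention at p < .05. The logistic GLMM for smoking behavior was not simulated, so no figure is offered for it. The change should be made: the remedy is cheap and the affected contrasts feed the go/no-go decision.

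**What to change.** Take all arm contrasts from one pre-specified model with covariate main effects and no data-selected arm-by-covariate terms, and delete the drop-if-non-significant rule for that model. Test moderation, parental smoking first, in a separate exploratory model that does not feed back into the arm contrasts. This keeps the question that motivated the blocking.

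If interactions are to stay in the primary model, then:
- mean-center every covariate column, including the parental dummies, or report a marginal contrast averaged over the covariates;
- use the same retained terms for all three arm comparisons on an outcome.

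The cost is SAP wording and a separate moderation table.

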**Participants.** We propose to study 150 adolescents (expected mean age = 13) enrolled in high school as a freshman or sophomore. Reflecting the demographics of the community in which we are recruiting, we expect approximately 70% of the sample to be at or below the poverty level, balanced between males and females, with the majority from an ethnic minority background. [name] previous work among adolescents suggests that at this age, smoking rates are very low. Among a sample of 185 adolescents, only 3.8% reported smoking regularly and 87% reported having smoked once ever, or never at all. In sum, we do not believe that smoking status at this age is a problem, however, our targeted enrollment (N = 150) has accounted for the possibility of having to drop current smokers in the final analyses as well as attrition.

**Feasibility.** [name] has experience working with low-income youth, and we plan to engage the following recommended best practices to ensure sufficient recruitment and retention. We attach letters of support from local high schools and community centers who serve individuals with characteristics suitable to our study. The headmasters of two local high schools have demonstrated enthusiasm for our study and plan to provide both institutional and social support in our endeavor. Additionally, we have budgeted for financial compensation for all components of the study (assessments and interventions), as well as snacks for the intervention sessions in order to improve enrollment and retention. The following projects and published studies demonstrate the productivity and preparedness of our research team for investigations in the impact of WM and mindfulness training on risk factors and smoking-related outcomes in at-risk youth. [name] is a developmental psychologist and expert in the acquisition and longitudinal study of low-income youth. Her work focuses on documentation of the effects of stress in this population. She has examined the impact of poverty on

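### The repeated-measures logistic model for actual smoking is likely to break down on sparse data: no onset rate is stated, an all-zero baseline leaves the time effect without a finite estimate, and no sparse-data method is planned

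*SAP*

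**What the plan says.** SAP, Data Analysis, item 3, adds WM and DT to multilevel models for three proximal risk measures and for actual smoking. For the last, "smoking behavior is dichotomous, so it will be analyzed using a GLMM with a logistic linking function". Each of WM and DT is split into a between-subject and a within-subject part, giving four terms, and item 3 interprets those coefficients.

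The opening paragraph of Data Analysis applies to all models. It sets a repeated-measures ANOVA structure over time, and "The 3 treatment conditions will be coded using 2 dummy variables contrasting each active treatment with control". Parental smoking (dummy coded), peer smoking and sensation seeking are named as example covariates. Arm-by-covariate interactions are fitted first and dropped if non-significant.

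The Power Analysis section states: "We assumed 150 total participants with 33% missing data"; "We also assumed 6 covariates in each of the models"; "Alpha was set at .05". For the smoking model it claims more than .80 "power to detect an effect size $\omega = .23$ or larger".

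In the Protocol, the Design Overview says: "The study design calls for block randomization of 150 non-smoking adolescents to one of three intervention conditions". The Participants paragraph calls smoking rates at this age very low. It cites an earlier sample of 185 in which "only 3.8% reported smoking regularly" and 87% had smoked once or never, and it allows for dropping current smokers from the final analyses. In the assessment table, timeline follow-back and carbon monoxide appear at baseline and 1 month only, and WM and DT at baseline and 1 week only. Parental smoking has four categories.

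Neither document states an expected number of new smokers, or a rule for separation or non-convergence.

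**The concern.** A logistic model fitted by maximum likelihood needs events spread across the levels of its predictors. Where a predictor, or a combination of predictors, splits events from non-events, at least one coefficient runs to infinity. Software then reports non-convergence, or a very large odds ratio with a Wald p-value that means nothing.

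Two features of the plan point that way. The baseline visit may contain no events at all, and the 1-month visit probably contains few.

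This is the only planned model for actual smoking. The Protocol's Benchmarks section counts significant benefit on measures of smoking risk or behaviour towards the case for a larger trial. A chance pattern, such as no events in one arm, could be read as a very large effect or as none. Dropping non-significant interactions would also be steered by unreliable Wald tests.

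**Working it through.** **The plan's own figure.** The smallest detectable omega with 1 df, two-sided alpha .05 and power .80 is (1.960 + 0.842)/√N.
- N = 150: 2.802/12.247 = 0.229, which rounds to the printed .23.
- N = 100 (33% missing): 2.802/10 = 0.280.

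The printed value is therefore reproduced only with no missing data, no covariates and no base rate. It says nothing about how many events are needed. In a contrast of two equal arms with overall rate r, the largest possible phi (every event in one arm) is √(r/(1−r)). At r = 5% that is √(.05/.95) = 0.229, and at 3.8% it is √(.038/.962) = 0.199. Below about 5%, an effect of .23 cannot occur in such a contrast.

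**Baseline rows.** Write the logit as a + u at baseline and c + u at 1 month, with time effect c − a. If every baseline value is 0, hold c fixed and let a fall. The baseline likelihood rises towards 1 and never reaches its maximum, so c − a has no finite estimate. One informative binary value per person remains, which barely identifies the variance of u. No onset rate enters this argument.

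**Events at 1 month.** Expected events = N × rate. Onset is an assumption, shown as a range; 3.8% is included only because it is a printed rate. Equal allocation is also assumed (50 per arm; about 33 per arm with a third missing). P(at least one arm has no events) = 1 − [1 − (1 − p)^n]³. For p = .038 and n = 50: .962^50 = .144, and 1 − .856³ = .37.

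| Onset | Events, 150 / 100 | Some arm has no events, 50 / 33 per arm |
|---|---|---|
| 1% | 1.5 / 1.0 | .94 / .98 |
| 2% | 3 / 2 | .74 / .89 |
| 3.8% | 5.7 / 3.8 | .37 / .62 |
| 5% | 7.5 / 5 | .21 / .46 |
| 10% | 15 / 10 | .015 / .09 |
| 13% | 19.5 / 13 | .003 / .03 |

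This probability exceeds one half only below about 3.1% onset (50 per arm) or 4.7% (33 per arm).

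**Separation in any term.** Trials were simulated at 1 month only, and separation was detected by linear programming: does a non-zero b exist with (2y − 1)Xb ≥ 0 in every row? Model A has an intercept, 2 arm dummies, 3 parental dummies, peer smoking and sensation seeking, with no true effects. Its ranges span a 50/20/20/10% parental mix (higher figure) and equal quarters (lower figure). Model B has 2 arm dummies, 6 covariates and the 4 WM/DT terms (600 runs per setting, two covariate-effect settings). All covariate distributions are assumed.

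| Onset | A: 150 observed | A: about 100 observed | B: 150 | B: about 100 |
|---|---|---|---|---|
| 3.8% | 76–84% | 91–94% | 76–82% | 93–94% |
| 5% | 51–69% | 78–90% | 66–70% | 84–88% |
| 10% | 10–33% | 33–59% | 18–28% | 39–53% |

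At 1–2% onset, model B separates in at least 95% of runs. With all the initial arm-by-covariate interactions added, some term separates in at least 97% of runs at every rate from 1% to 13%. Baseline rows were left out throughout.

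**The case against.** A reader might infer more: that the model will usually give infinite arm estimates, or that 150 non-smokers cannot produce enough events. The documents do not support either.

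- **Any term is not the arm term.** The high percentages count separation in any coefficient, often a parental-smoking dummy. That does not by itself make an arm odds ratio infinite. An arm with no events is the majority outcome only at the low onset rates given above. Item 3 also interprets the WM and DT coefficients, not the arm contrasts.
- **The onset rate is unknown.** 3.8% is a prevalence of regular smoking. The outcome may count any smoking over roughly three months (8 weeks of intervention plus 1 month). The same earlier sample implies that 13% had smoked more than once (100 − 87), also a prevalence. True onset could be lower or higher than 3.8%, and no required event count follows from the documents.
- **The all-zero baseline is conditional.** No eligibility rule is printed, and the Protocol foresees possibly dropping current smokers, so some may be enrolled. The Design Overview mentions smoking behaviour only at 1 month, and the SAP does not say that baseline smoking is an outcome row.
- **Other inputs are inferred.** The 33% is a power assumption, not a forecast of 1-month dropout. The covariates are given as examples, and no parental-smoking mix is stated.
- **Three of the four Aim 3 outcomes are unaffected.**

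All of this stands as a limit on the claim. It does not supply an onset rate or a sparse-data method, and it leaves separation likely at low onset.

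**Conclusion.** Wrong as written, within limits. If baseline smokers are screened out or dropped and baseline is an outcome row, the time effect in the planned GLMM has no finite estimate at any onset rate. At an assumed onset of 1–5%, the 1-month part of the model separates in at least one term in more than half of simulated trials, and in about nine in ten or more at 3.8% with a third missing. At 10% onset, separation is a minority event if all 150 are observed, and ranges from a third to somewhat over half if about 100 are. Infinite arm estimates are a smaller risk: 37–62% at 3.8% and 2–9% at 10%. These figures rest on assumed onset, equal allocation and assumed covariate distributions. The plan contains nothing to handle the problem if it occurs.

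**What to change.** Replace the smoking GLMM with a Firth-penalised logistic regression of 1-month smoking among baseline non-smokers, with profile penalised-likelihood intervals.

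1. Fit one model with the two arm dummies and at most one binary covariate (any current parental smoker).
2. To keep item 3's question, fit separate models that each add one WM or DT score: either the change from baseline to 1 week, or the 1-week value adjusted for baseline. The SAP should name one. The change score costs one parameter; the adjusted value costs two.
3. Report event counts by arm with exact intervals, and state the assumed onset rate.
4. Label the smoking analysis descriptive, and do not let it alone satisfy the Aim 3 benchmark.

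The cost is SAP wording and standard software. For this outcome the plan gives up full covariate adjustment, arm-by-covariate interactions and the within/between split of WM and DT. Penalisation makes the estimates finite but does not restore power. With 50 per arm, power to detect a halved rate is 0.08 from 3.8% and 0.155 from 10%, which is why the analysis should be descriptive.
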